10.6.4 Monitoring of patients with increased lipase and/or amylase >2x ULN

Potential safety signals for acute pancreatitis have been identified in the post-marketing experience of other GLP-1 receptor agonists. Therefore, patients enrolled in this study should be followed for any suspected pancreatitis, eg, with symptoms and/or signs of acute abdominal distress or abnormal levels of pancreatic enzymes. Serum amylase and lipase concentrations are monitored routinely at screening, baseline and periodically during the study treatment period.

In the presence of clinical signs and/or symptoms evocative of pancreatitis, eg, persistent abdominal pain, which can radiate to the back, often with characteristic positional features, with possible occurrence of nausea, vomiting, fever and leukocytosis, further measurement of amylase and lipase should be performed. The clinical signs and/or symptoms should be documented in the source data.

(1) Elevation of Amylase and/or Lipase >2x ULN without clinical signs and/or symptoms

In any case where amylase and/or lipase are >2x ULN, a retest (centrally assessed as far as possible) must be performed as follows:

- If value(s) is/are >2-3x ULN: retest within 7 days;
- If value(s) is/are >3x ULN: retest within 48 hours;
- If the value(s) remain(s) >2x ULN upon retesting: amylase and/or lipase levels should be retested weekly until values are <2x ULN.

In case a retest is >2x ULN a gastroenterological evaluation and imaging (ultrasound and/or CT or MRI with contrast, as appropriate) must be performed. Please document in the source data the absence of clinical signs and/or symptoms (if clinical signs and/or symptoms develop, please see part (2) below).

Best clinical judgment is to be used when interpreting elevated serum amylase and lipase levels in asymptomatic patients. Temporary discontinuation of the IMP may be considered in these cases if deemed necessary by the Investigator.

(2) Elevation of Amylase and/or Lipase >2 x ULN with clinical signs and/or symptoms

In the presence of clinical signs and/or symptoms evocative of pancreatitis (as described above) associated with elevated amylase and/or lipase, treatment with the IMP should be promptly and at least temporarily discontinued pending further clinical evaluation and diagnosis confirmation.

Clinical signs and/or symptoms are to be documented in the source data. A laboratory determination of amylase and lipase has to be obtained at the time of the event and again within 48 hours or earlier as clinically indicated. If the value(s) remain(s) >2x ULN, then amylase and/or lipase levels should be retested as described in (1) above, or more often if clinically indicated.

A gastroenterologic evaluation and imaging (ultrasound and/or CT or MRI with contrast, as appropriate) must be performed. If a diagnosis of pancreatitis is confirmed, IMP should not be restarted and should be permanently discontinued.

In both cases as described above under (1) and (2), all laboratory or clinical documentations are to be collected. If the retest confirms lipase and/or amylase values are >2x ULN, the event must be reported in the e-CRF on the specific AE form for “Increased Lipase and/or Amylase >2x ULN” and the specific forms, using the appropriate verbatim: eg, “increased amylase and/or lipase” in case of isolated enzyme elevation, “suspected pancreatitis” in the presence of clinical signs evocative of pancreatitis if the diagnosis is suspected but cannot be confirmed or excluded, and “pancreatitis” if the diagnosis has been confirmed.

The PSAC will review selected pancreatic events, including pancreatitis, pancreatic neoplasms and abnormal levels of amylase or lipase.

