6.4.3 Pancreatic Safety Assessment Committee (PSAC)

Potential safety signals for acute pancreatitis have been identified in the post-marketing experience with other GLP-1 receptor agonists. Specific monitoring for pancreatic events is planned in this study (see [Section 10.6.4](#)) and a Pancreatic Safety Assessment Committee (PSAC) has been set up. This is a committee of experts in the field of pancreatitis and pancreatic neoplasm, independent from the Sponsor and the Investigators, implemented to assess pancreatic events that may occur during the study. The PSAC will review selected pancreatic events, including pancreatitis, pancreatic neoplasms and abnormal levels of amylase or lipase. This review will be conducted in a blinded manner with regard to study treatment. A detailed charter describes the PSAC procedures.

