2.1.4.2 Adverse events variables

Adverse event observation period

- Pre-treatment adverse events are AEs that developed or worsened or became serious from the signed informed consent date up to first injection of open-label IMP.
- Treatment-emergent adverse events are AEs that developed or worsened (according to the Investigator’s opinion) or became serious during the period from the administration of first dose of the study treatment up to 3 days (9 days for the weekly GLP1) after the last administration.
- Post-treatment adverse events are AEs that developed or worsened or became serious during the post-treatment period.

All AEs (including SAEs and AEs with prespecified monitoring) will be coded to a lower-level term (LLT), preferred term (PT), high-level term (HLT), high-level group term (HLGT), and associated primary system organ class (SOC) using the version of Medical Dictionary for Regulatory Activities (MedDRA) currently in effect at Sanofi at the time of database lock.

Record the occurrence of AEs (including SAEs and AEs with prespecified monitoring) from the time of signed informed consent until the end of the study.

AESI, AE requiring specific monitoring, or specific AEs to be analyzed:

- Local tolerability at injection site: identified by searching the term “injection site” in either the PTs coded from the investigator reported terms or the PTs coded from the Allergic Reaction Assessment Committee (ARAC) diagnosis terms.
- Allergic or allergic-like reactions: events recorded on the AE form for “suspected allergic reaction” and its associated complementary forms. Allergic reaction or possible allergic reaction will be adjudicated by the ARAC.
- Increased pancreatic enzymes > 2 x ULN/suspected pancreatitis: all events confirmed by a repeated test recorded on the AE form for “increased lipase and/or amylase greater than 2 x

ULN” and its associated complementary forms. All events reported will be sent to Pancreatic Safety Assessment Committee (PSAC) for adjudication of pancreatitis.

- Pancreatic neoplasm: All pancreatic neoplasm related events (AEs of pancreas carcinoma, AEs of pancreas neoplasm benign or malignant AEs of pancreas neoplasm unspecified, AEs of pancreatic endocrine neoplasm/carcinoma, or AEs of pancreas mass, cyst, pseudocysts) will be reviewed, assessed and adjudicated by the PSAC for pancreatic neoplasm.

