 - The number (%) of patients with events reported on the AE form for increased lipase and/or amylase >2 times ULN and its associated complementary forms will be summarized by PTs for each treatment group, sorted by decreasing incidence of PT.
 - The number (%) of patients with events positively adjudicated as pancreatitis by the PSAC will be summarized by type: 1) acute pancreatitis, 2) acute exacerbation of chronic pancreatitis, 3) chronic pancreatitis, 4) unknown pancreatitis.

- All events sent to PSAC for adjudication of pancreatitis (ie, events reported on the AE form for increased lipase and/or amylase > 2 times ULN) will be listed along with the adjudication outcome.
- Pancreatic neoplasm
 - All the events sent to PSAC for adjudication for pancreatic neoplasm will be listed along with the adjudication outcome including PSAC diagnosis, type of neoplasm (malignant, benign, not determined), cancer stage etc.

Increased calcitonin

The number (%) of patients with events reported on the AE form for increased calcitonin ≥ 20 pg/mL and its associated complementary forms will be summarized by PTs for each treatment group, sorted by decreasing incidence of PT in the FRC group. In addition, a listing of those patients will be provided.

ALT increase

The number (%) of patients with events reported on the AE form for ALT increase and its associated complementary forms will be summarized by PT for each treatment group, sorted by decreasing incidence of PT in the FRC group. In addition, a listing of those patients will be provided.

Device-related events

The number (%) of patients with events reported on device-related event questionnaire will be summarized for each treatment group along with 2 subcategories, events associated with a clinical event (either symptomatic hypoglycemic event or adverse event) and events not associated with a clinical event. The number of events and rates in patient year will also be summarized as appropriate. The number (%) of patients who have device-related events with lixisenatide dose $< 5 \mu\text{g}$, $> 20 \mu\text{g}$ within the corresponding time window (from event start date to event end date or to treatment end date if event end date is missing) of device-related event will be summarized for FRC group only. In addition, a listing of patients with those events will be provided.

Analysis of pre-treatment and post-treatment adverse events

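### Pancreatitis diagnosed on imaging has no written route to PSAC adjudication when both enzymes are at or below 2x ULN on the retest

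*Protocol*

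**What the plan says.** Protocol 10.6.4 separates enzyme rises without symptoms, case (1), from those with symptoms, case (2). In case (2) two samples are needed: "A laboratory determination of amylase and lipase has to be obtained at the time of the event and again within 48 hours or earlier". It continues: "A gastroenterologic evaluation and imaging (ultrasound and/or CT or MRI with contrast, as appropriate) must be performed. If a diagnosis of pancreatitis is confirmed", followed by the rule on permanent discontinuation of IMP. In case (1), by contrast, imaging is called for only when a retest is above 2x ULN.

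The reporting rule then covers both cases together: "In both cases as described above under (1) and (2), all laboratory or clinical documentations are to be collected". The next sentence reads: "If the retest confirms lipase and/or amylase values are >2x ULN, the event must be reported in the e-CRF on the specific AE form". That same sentence lists the terms to enter on the form, including one for suspected pancreatitis and one for confirmed pancreatitis. Table 2 (Protocol 10.4.5) ties the specific form to a confirmed enzyme increase and has no row for pancreatitis itself.

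SAP 2.1.4.2 defines the category of raised enzymes and suspected pancreatitis as "all events confirmed by a repeated test recorded on the AE form" for the enzyme rise, and sends the events so reported to PSAC. SAP 2.4.5.2 describes the listing as "All events sent to PSAC for adjudication of pancreatitis (ie, events reported on the AE form for increased lipase and/or amylase" above 2 times ULN; Protocol 11.4.6.2 uses the same definition. The adjudicated result is the number and percentage of patients with pancreatitis confirmed by PSAC, by type.

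The remit is worded more broadly. Protocol 6.4.3: "The PSAC will review selected pancreatic events, including pancreatitis, pancreatic neoplasms and abnormal levels of amylase or lipase". Protocol 10.4.1.4 also names pancreatic events beside enzyme rises, and refers to 10.6.4 for the rule. Protocol 6.4.3 says that the committee's procedures are in a charter.

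**The concern.** The protocol set up PSAC because of pancreatitis signals with this drug class. The trial is open-label, and Protocol 8.3.1 lists blinded review by the adjudication committees among the measures that compensate for the lack of blinding. A pancreatitis case that does not reach PSAC rests on the assessment of an investigator who knows the treatment.

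The plan makes a laboratory retest the entry ticket to that review. A persistent enzyme rise without symptoms is adjudicated, while a clinical and imaging diagnosis can be left out if the enzymes have fallen. The plan's other adjudicated events have no such gate. SAP 2.1.4.2 sends pancreatic neoplasm events to PSAC by type of adverse event, and Protocol 6.4.2 sends allergic and possibly allergic events to their committee on suspicion. The gap can only remove cases from the adjudicated pancreatitis count; it cannot add any.

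**Working it through.** The plan states no figure on this point, so the check is a trace of the written pathway.

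**Inputs**
- Trigger for the specific form: retest of amylase and/or lipase above 2x ULN, in both cases (Protocol 10.6.4).
- Imaging in case (2): required whatever the retest shows (Protocol 10.6.4).
- Category analysed: events confirmed by a repeat test and recorded on that form (SAP 2.1.4.2).
- Set sent to PSAC for pancreatitis: events on that form (Protocol 11.4.6.2, SAP 2.4.5.2).

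**Trace for a symptomatic patient whose first value is above 2x ULN**

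| Retest | Imaging diagnosis | Specific form required | In the set sent to PSAC |
|---|---|---|---|
| Either enzyme above 2x ULN | No | Yes | Yes |
| Either enzyme above 2x ULN | Yes | Yes | Yes |
| Both at or below 2x ULN | No | No | No |
| Both at or below 2x ULN | Yes | No | No |

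The last row is the gap. The protocol allows this state, because in case (2) imaging goes ahead whatever the retest shows. By the same definitions, a patient with diagnosed pancreatitis whose enzymes never exceeded 2x ULN has no written route either. That patient falls outside the heading of case (2), so this is a secondary consequence of defining the PSAC set by the enzyme form.

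**How often.** The documents give neither the expected number of pancreatitis cases nor the chance that both enzymes fall to 2x ULN or below by the retest. Write k for the number of true symptomatic cases and p for that chance, with cases independent. The chance that at least one case misses adjudication is 1 − (1 − p)^k. For assumed p from 0.1 to 0.5:
- k = 1: 10% to 50%
- k = 2: 1 − 0.9² = 19% to 1 − 0.5² = 75%
- k = 3: 1 − 0.9³ = 27% to 1 − 0.5³ = 88%

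Both inputs are assumptions. The range is too wide to serve as an estimate and shows only that the answer depends on a rate that is not given.

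**The case against.** - **The trigger is an if, not an only if.** Protocol 10.6.4 taken alone makes a confirmed retest sufficient for the form and does not forbid using the form otherwise. That is fair for the one sentence. It does not survive SAP 2.1.4.2, which restricts the category to confirmed events, or the definition in Protocol 11.4.6.2 and SAP 2.4.5.2, which equates the PSAC set with that form.
- **Other sections are broader.** Protocol 10.4.1.4 and the safety endpoints in 9.2.2 mention pancreatic events. Section 10.4.1.4 refers back to 10.6.4, where the retest condition sits, and neither gives a separate route. The wording shows a wider intention but does not carry it out.
- **The charter may cover it.** This stands. The charter was not supplied and may select pancreatitis by diagnosis. The protocol and SAP definitions would then still need to be brought into line with it.
- **The loss is limited.** This stands too. Both enzymes must be at or below 2x ULN, and a sample taken earlier than 48 hours may still be raised. The case remains in the general treatment-emergent tables, in the serious event tables if serious, and, because confirmed pancreatitis ends treatment, in the discontinuation tables. Safety analysis is descriptive and no tested endpoint is touched.

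A reader might also see a contradiction with Protocol 10.3.3, which makes confirmed acute pancreatitis a reason to stop IMP. That section is a withdrawal rule and says nothing on forms or adjudication, so the two can differ without conflict. Nor do the documents show bias between arms: the rule applies equally to both.

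**Conclusion.** The gap is real on the written plan. An imaging diagnosis of pancreatitis with both enzymes at or below 2x ULN on the retest has no stated path to PSAC, its listing or the adjudicated table, while the remit in Protocol 6.4.3 includes pancreatitis as such. This rests on reading Protocol 10.6.4 together with SAP 2.1.4.2, SAP 2.4.5.2 and Protocol 11.4.6.2, and on the charter not supplying another route.

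The direction is known: the adjudicated count can be too low, never too high, because of this. The size is unknown. It is tempting to say that one missed case among a few would understate incidence by a given percentage, but that takes the miss for granted and the documents give no rate for it. Nor would such a case vanish from the trial's safety data; it would be missing from the blinded, adjudicated part. The point merits a low-cost correction of the reporting and adjudication definitions and does not threaten the trial's main conclusions.

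**What to change.** In Protocol 10.6.4 and Table 2, require the specific form and PSAC submission for either of two triggers: a confirmed rise of amylase and/or lipase above 2x ULN, or any pancreatitis that the investigator reports as suspected or confirmed, whatever the retest or peak enzyme value. Amend the category in SAP 2.1.4.2 and the definition of the PSAC set in Protocol 11.4.6.2 and SAP 2.4.5.2 to match, and check that the charter agrees.

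Optionally, add a search of preferred terms for pancreatitis before database lock, so that any case entered only on the general form is found. This would be a new step. SAP 2.1.4.2 lists the types of neoplasm event to be adjudicated but describes no such search for them.

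The cost is a few sentences, an instruction for completing the e-CRF, and a few extra cases for a committee that already exists. The change concerns reporting and adjudication only; no dosing, stopping, retest or imaging rule is altered.

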10.6.5 Management of patients with increased calcitonin values

During the course of the study, if a calcitonin value is found ≥ 20 pg/mL (5.9 pmol/L):

- A retest should be performed by the central laboratory within 7 days. In addition, blood should be collected and sent to the central laboratory for measurement of: calcium, phosphorus, gastrin, Thyroid Stimulating Hormone (TSH), and anti-thyroid peroxidase (anti-TPO) antibodies;
- The clinical and laboratory documentations listed below are to be collected and recorded in source documents as soon as possible:
 - Potential false positive circumstances: smoking status, proton-pump inhibitor treatments (eg, omeprazole), autoimmune thyroid diseases (Hashimoto's thyroiditis or Graves' disease), differentiated thyroid cancer, hypercalcemia, hypergastrinemia, chronic renal insufficiency (not on dialysis), other neuro-endocrine tumors (small cell lung cancer, intestinal carcinoid), acute pulmonary inflammatory conditions, or sepsis.
 - Specific personal and/or familial medical history in relation to thyroid or other endocrine diseases;
 - Specific physical examination (neck, thyroid gland).

If the retest confirms that the calcitonin value is ≥ 20 pg/mL:

- The event must be reported in the e-CRF on the specific AE form and specific complementary form for "increased calcitonin ≥ 20 pg/mL" with all appropriate clinical and laboratory documentation.
- An ultrasound scan of the thyroid should be performed and the patient may be referred to a thyroid specialist if judged necessary.
- The patient should continue to be followed according to protocol schedule (including planned calcitonin measurements). The specific AE form "increased calcitonin ≥ 20 pg/mL (5.9 pmol/L)" should be updated with any new information collected during the follow up.
- If a calcitonin value ≥ 50 pg/mL (14.75 pmol/L) is found at any time during further follow up, the patient should be permanently discontinued from IMP (see [Section 10.3.4](#)) and referred to a specialist. As far as possible, blood should be collected 1 to 2 weeks after IMP discontinuation and sent to the central laboratory for calcitonin measurement.
- If at any time during follow-up a calcitonin value ≥ 20 pg/mL increases by 20% or more between 2 assessments (while remaining below 50 pg/mL), a repeated measurement should be performed earlier than scheduled in the protocol, ie, 1 month later. Once results are available, discussion with Sponsor should be initiated without delay for further guidance.

10.6.6 Monitoring of renal function in case of prolonged and severe nausea and vomiting

In case of prolonged or severe nausea and vomiting, if clinically indicated, serum creatinine measurement has to be centrally performed. If there is an acute increase of serum creatinine, metformin has to be discontinued until resolution of renal dysfunction.

10.6.7 Follow-up of laboratory abnormalities

Decision trees for the management of certain laboratory abnormalities are provided in [Appendix B](#).

10.6.8 Monitoring of device-related events

A device-related event (DRE) includes any suspected problem with the injection device(s) used in the study which has or may lead to a health hazard (eg, adverse event). Typical problems include pen performance failure, patient (or caregiver) having difficulty understanding the instructions or using the pen or auto-injector, use error, etc.

Examples of device-related events include but are not limited to:

- Dosing problems: jamming, inability to inject, partial injection, need to repeat injection, dosage knob stuck;
- Needle issues: difficulty attaching the needle;
- Breakage of the pen;
- Mix-up of pens/devices (patient injects using a pen/device different than the intended one);
- Difficulty to understand the instructions in the product instructions leaflet;
- Use error: Incorrect use of the pen/device by the patient/caregiver/healthcare provider.

Device-related events will be pro-actively monitored during the study by asking at each study visit whether the patient/caregiver experienced any DRE. If answer is yes, the specific e-CRF Device-Related Event Questionnaire (DREQ) will be completed.

If the device-related event is associated with a symptomatic hypoglycemic event, a hyperglycemic adverse event or another adverse event, the corresponding symptomatic hypoglycemic forms or adverse event forms must also be completed. This associated adverse event will be qualified as a serious adverse event only if it fulfills seriousness criteria, and in this case, the SAE reporting procedure (see [Section 10.4.3](#), Instructions for reporting serious adverse events) should be followed.

As needed, further instruction and troubleshooting guidance should be provided to the patient by the study site according to the instructional materials/troubleshooting guide provided by the Sponsor.

For device-related events, related to Solostar Pen for patients on FRC, that are not resolved by further guidance/review of instructions or troubleshooting with the pen during the visit (on site visit or phone visit), a PTC form must be completed, the pen associated with the event should be

retrieved, and both should be sent to the manufacturing site for technical investigation and determination of the root cause.

10.7 ADVERSE EVENTS MONITORING

All events will be managed and reported in compliance with all applicable regulations, and included in the final clinical study report.

11 STATISTICAL CONSIDERATIONS

11.1 DETERMINATION OF SAMPLE SIZE

The sample size calculations are based on the primary efficacy variable change in HbA1c from baseline to Week 26 and intent-to-treat (ITT) analysis, with the following assumptions:

- A common standard deviation of 1.1%;
- A 0.4% mean difference between FRC and GLP-1 receptor agonist in change in HbA1c from baseline to Week 26;
- A drop-out rate of 20%; The FRC dropped patients are assumed to respond the same as the control patients, ie, no treatment difference between the FRC dropped patients and the control patients;
- A t-test at a 2-sided 5% significance level with at least 90% power.

Based on the above assumptions, 500 patients (250 per group) are needed for this study.

Calculations were made using nQuery Advisor® 7.0.

